## PROTOCOL SYNOPSIS

Title: **A Randomised, Adaptive Design, Double-Blind (3rd Party Open), Placebo Controlled, Sequential Group Study to Determine the Safety, Tolerability, Pharmacokinetics and Efficacy of Twice Daily Application of a Topical ZPL-5212372 (1.0% w/w) Ointment Administered for up to 2 Weeks in Adult Healthy Volunteers and Patients with Moderate to Severe Atopic Dermatitis**

Sponsor Study No: ZPL521/101

No:

Compound: ZPL-5212372

Phase: Phase 1/2a

Sponsor: Ziarco Pharma Ltd

Principal Investigator:

Objective(s): Primary  
Cohorts 1 and 2  
To assess the safety and tolerability, local and systemic, of ZPL-5212372 administered as a topical ointment (containing 1.0% (w/w) concentration of ZPL-5212372) twice daily, for 1 week, to healthy subjects and patients with moderate to severe atopic dermatitis (AD).

Cohort 3  
To evaluate the efficacy of ZPL-5212372 administered as a topical ointment (containing 1.0% (w/w) concentration of ZPL-5212372) twice daily, for 2 weeks, to patients with moderate to severe AD.

Secondary  
Cohorts 1 and 2  
To investigate the systemic pharmacokinetics of ZPL-5212372 following single and multiple dose topical applications of a 1.0% (w/w) concentration of ZPL-5212372 ointment, administered twice daily, for 1 week, to healthy subjects and patients with moderate to severe AD.

Cohort 3  
To assess the safety and tolerability, local and systemic, of ZPL-5212372 administered as a topical ointment (containing 1.0% (w/w) concentration of ZPL-5212372) twice daily, for 2 weeks, to patients with moderate to severe AD.

To investigate the trough concentrations of ZPL-5212372 in patients with moderate to severe AD following twice daily applications of ZPL-5212372 administered as a topical ointment (containing 1.0% (w/w) concentration of ZPL 5212372).

Exploratory  
Cohorts 1 to 3

To explore the subjects perception of the Ziarco development ointment formulation using the Ziarco Ointment Questionnaire.

**Design:** This is a randomised, adaptive design, double-blind (3rd party open), placebo controlled, sequential group study to determine the safety, tolerability, PK and efficacy of twice daily application of topical ZPL-5212372 (1.0% w/w) ointment administered as a 2:1 ratio for active and placebo groups. This study will consist of 3 sequential cohorts each separated by formal safety reviews.

All subjects (both healthy volunteers and AD patients) will be required to attend a screening visit(s) to confirm suitability to enter the study. In order to be eligible AD patients must have moderate-severe AD, defined as:

- Eczema Area and Severity Index (EASI) of  $\geq 9$  and  $\leq 48$
- Body surface area involvement (BSA) of between 10% and 40%
- Investigator Global Assessment Score (IGA) of at least 3 (moderate disease)
- Active disease for at least 6 months at the time of randomisation

All AD patients will be required to switch to twice daily application of study emollient (instead of their usual emollient) for at least 7 days prior to randomisation (Day 1).

Subjects will attend the clinic on Day 1. If all inclusion/exclusion criteria are met subjects will be randomised to receive either topical 1.0% (w/w) ZPL-5212372 ointment or matching placebo ointment twice daily, for either 7 days (Cohorts 1 and 2) or 14 days (Cohort 3).

Cohort 1 will consist of 12 healthy adult volunteers, dosed twice daily for 7 days as in-patients. An initial sentinel group (n=3) will have study ointment applied over 10% BSA. After 48 hours of dosing (i.e. 4 applications) the safety data will be reviewed. Provided that the study ointments are well tolerated the remainder of the cohort (n=9) may start dosing with coverage of 40% BSA with study ointments. Assessments will be conducted on a daily basis as described in Sections 6 & 7. Subjects will remain in the clinic until Day 9 assessments are complete.

Cohort 2 will consist of 12 moderate to severe AD patients, dosed twice daily for 7 days as in-patients. An initial sentinel group (n=3) will have study ointment applied over 10% BSA. After 48 hours of dosing (i.e. 4 applications) the safety data will be reviewed. Provided that the study ointments are well tolerated the remainder of the cohort (n=9) may start

dosing with coverage of 40% BSA with study ointments. Assessments will be conducted on a daily basis as described in Sections 6 & 7. Patients will remain in the clinic until Day 9 assessments are complete.

Cohort 3 will consist of 30 moderate to severe AD patients, dosed twice daily for 14 days as out-patients. Up to a maximum of 50% BSA of AD lesioned skin may be treated with study ointments. Patients will return to the clinic following their Baseline visit (Day 1) on Day 5, Day 8, Day 10 and Day 15 for the assessments described in Sections 6 & 7.

All subjects (both healthy volunteers and AD patients) will be required to have a follow up visit 7-14 days following their last application of study ointment.

Treatment: Each subject will be treated with 1.0% (w/w) ZPL-5212372 ointment or matching placebo, topically applied to the skin twice daily.

Number of Subjects: Cohort 1  
Sufficient subjects will be screened to achieve approximately 12 randomised and evaluable subjects.

Cohort 2  
Sufficient patients will be screened to achieve approximately 12 randomised and evaluable patients.

Cohort 3  
It is anticipated that approximately 45 patients will be screened to achieve approximately 30 randomised and evaluable patients.

Population: Cohort 1  
Healthy volunteer adult subjects (18 to 55 years).

Cohorts 2 and 3  
Adult subjects (18 to 65 years) with moderate to severe atopic dermatitis.

Efficacy Endpoints: Cohort 3 Only  
Primary Endpoints:  
Percentage change from baseline in the Eczema Area and Severity Index (EASI) score  
Secondary Endpoints:  
Change from baseline in the Numerical Rating Score (NRS) for Pruritus (Worst Itch) over 24 hours  
Change from baseline in the NRS for Sleep Disturbance  
Change from baseline in Duration of Itching  
Change from baseline in Verbal Rating Score (VRS) for Pruritus  
Change from baseline in BSA  
Reduction in Investigators Global Assessment (IGA) Score (subject will be deemed to have had a response with a reduction from baseline of at least 2 points)  
Patient Global Impression of Change (PGIC)

Safety Endpoints:	
Cohort 1 Adverse events, local tolerance assessments, supine vital signs (blood pressure (BP) and pulse rate), 12-lead ECG, laboratory safety tests (clinical chemistry, haematology and urinalysis).
 
Cohorts 2 and 3 Adverse events, supine vital signs (BP and pulse rate), 12-lead ECG, laboratory safety tests (clinical chemistry, haematology and urinalysis).

Exploratory Endpoints:	
Cohorts 1 to 3 Subject responses to Ziarco Ointment Questionnaire.

Pharmacokinetic Endpoints:	
Cohorts 1 and 2 ZPL-5212372 plasma concentrations Day 1 (sd): <math>AUC_{\tau}</math>, <math>C_{max}</math> and <math>T_{max}</math> ZPL-5212372 plasma concentrations Day 7 (ss): <math>AUC_{last}</math>, <math>AUC_{\tau}</math>, <math>C_{max}</math>, <math>T_{max}</math>, and <math>t_{1/2}</math>. Observed accumulation ratios based on <math>AUC_{\tau}</math> and <math>C_{max}</math>
 
Cohort 3 Trough Plasma ZPL-5212372 concentrations

Statistical Methods:	
Separate randomisation codes will be generated for each cohort. The randomisation for Cohort 3 will be stratified by EASI score (<math>EASI \leq 20</math> and <math>EASI \geq 20</math>).
 
All statistical testing for Cohort 3 efficacy data will be at the 5% level of significance (1-sided) and all point estimates for the comparison between treatment groups will be accompanied by 2-sided 90% confidence intervals. No adjustment will be made for multiplicity due to multiple endpoints/comparisons. No statistical testing will be performed with the data from Cohorts 1 and 2.
 
For change from baseline endpoints baseline is defined as the last measurement available prior to the start of dosing on Day 1.
 
Separate tables, listings and figures will be generated for each cohort and within each cohort endpoints will be summarized by treatment group and visit.
 
Safety data (adverse events, vital signs, ECG and laboratory data) will be summarized by treatment group and visit (where applicable) using all subjects in the Safety Analysis Set – defined as all randomised subjects who received at least one dose of study treatment. The incidence of treatment emergent adverse events will be tabulated regardless of severity and by maximum severity. Those events regarded as possibly treatment related by the investigator will be summarized separately. Changes from baseline in laboratory parameters, vital signs and ECG data will be summarized in addition to absolute values.
 
ZPL-5212372 concentrations (all cohorts) and parameters (Cohorts 1 and 2 only) will be summarized using all subjects in the Pharmacokinetic Set -

defined as all ZPL-5212372 treated subjects in the Full Analysis Set who have at least one ZPL-5212372 concentration recorded. The ZPL-5212372 pharmacokinetic parameters  $AUC_{inf}$ ,  $AUC_{last}$  and  $t_{1/2}$  will be calculated using non-compartmental methods.  $C_{max}$  and  $T_{max}$  will be determined directly from the data.

Individual profile and median plots will also be plotted. Median profiles for Cohorts 1 and 2 will be plotted by day.

Though some efficacy assessments are included for Cohort 2 the data will only be listed and no formal comparisons will be made between the treatment groups. Consequently efficacy will only be assessed for Cohort 3.

The Full Analysis Set (FAS) used for efficacy analyses will include all randomized subjects who received at least one dose of study treatment. A Per Protocol (PP) Analysis Set for a sensitivity analysis of the primary efficacy endpoint will include those subjects in the FAS who have not deviated from the protocol in such a way to influence their efficacy assessment.

The primary efficacy endpoint is the percentage change from baseline to Week 2 in the EASI score. The percentage changes from baseline in the EASI score at Week 2 will be summarized and analysed by ANCOVA. The difference between treatment groups in the percentage changes from baseline will be estimated, along with its 90% confidence interval. Baseline will be included as a continuous covariate in addition to treatment.

The proportion of subjects who achieve an EASI-50 response (50% reduction in EASI score from baseline) at Week 2 will be compared between the treatment groups. Group proportions and the difference between these proportions will be calculated along with the corresponding 90% confidence interval. These data will also be analysed using logistic regression, including treatment and baseline. The odds ratio and accompanying 90% confidence interval will be presented. The proportion of subjects who achieve an EASI-75 response (75% reduction in EASI) and the proportion of subjects who are responders for IGA score (reduction from baseline of at least 2 points) at Week 2, will be analysed using the same analyses described for the EASI-50 response.

The changes from baseline in body surface area, pruritus NRS score for worst itch, NRS score for sleep disturbance and duration of itching at Week 2 will be analysed using the same analyses described for the primary analysis. The changes from baseline in VRS score will be summarized using categorical shift tables. The PGIC score will be summarized and analysed using logistic regression, presenting odds ratios and associated 90% confidence intervals for the comparison between treatment groups.

Responses to the Ziarco ointment questionnaire will be summarized.

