## **8.6 Safety Analyses**

Safety data will be summarized by treatment group for each cohort using all subjects in the Safety Analysis Set.

No imputation will be used for handling missing data, with the exception of conservative approaches taken for missing adverse event information (e.g. intensity). Details of such conventions will be documented in the SAP prior to the study database being locked.

Adverse events will be coded using the MedDRA dictionary. The incidence of all treatment emergent adverse events will be tabulated by treatment group and by treatment group and severity. Those events regarded as possibly treatment related by the investigator will be summarized separately.

Changes from baseline in laboratory parameters, vital signs and ECG data will be summarized by visit for each treatment group.

For Cohort 1 only, local toleration assessed by the Draize score, will be summarized by visit for each treatment group. The changes from baseline in Draize score will also be summarized using categorical shift tables.

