### 6. GENERAL ASPECTS FOR STATISTICAL ANALYSIS

#### 6.1. GENERAL METHODS

All statistical tests for Cohort 3 will be 1-sided at the 0.05 level of significance and accompanied by a 2-sided 90% CI. There will not be any adjustments for multiple comparisons. No statistical testing will be performed with the data from Cohorts 1 and 2.

All summaries and listings will be presented by treatment group and by cohort. For Cohorts 1 and 2, adverse events and pharmacokinetic data will be presented by treatment group and BSA treated (10%, 40% and overall) to assess whether BSA impacts this data.

Only on-treatment records will be summarised for post-baseline visits, except follow-up, unless stated otherwise. A record is considered on-treatment if it is on or before the date of last study medication plus 1 day.

Continuous variables will be summarised using the number of observations (n), mean, standard deviation (SD), 95% Confidence interval (CI) of mean, median, minimum, and maximum. Geometric mean and coefficient of variation (CV) will be included for PK parameters, where appropriate. Categorical variables will be summarised using frequencies and percentages. The number of missing values will be presented in summary tables. The missing count will not include

SAP Version v2.0 Page 22 of 43

Date: 16th March 2017

subjects who have discontinued at earlier visits.

Unless otherwise specified, the estimated mean and median for a set of values should be printed out to 1 more decimal place than the original values, and standard deviations should be printed out to 2 more decimal places than the original values. The minimum and maximum should report the same number of decimal places as the original values. The coefficient of variation will always be reported as a percentage to 1 decimal place. Percentages will be displayed with 1 decimal place; except percentages will not be presented when the count is zero and 100% will be presented as an integer.

Unless stated otherwise, baseline will be defined as the last non-missing measurement prior to administration of the first dose of IMP.

In by-visit summary tables the baseline will be summarised using all available data, but also for each visit using only the baseline data from subjects with available data at the visit; hence the mean change from baseline will equal the mean visit value – mean baseline value.

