#### 10.4. LABORATORY EVALUATIONS

The change from baseline and percentage change from baseline in haematology, chemistry, and continuous urinalysis parameters will be summarised by treatment group using descriptive statistics. Discrete urinalysis parameters will be summarised with counts and percentages by treatment group. The number of normal and abnormal (low and high) records will also be summarised with counts and percentages by treatment group. Baseline and all protocol specified on treatment (i.e. on or before the date of last study medication plus 1) visit data will be summarised. If a baseline value is missing for a parameter, the screening value will be used as the baseline value.

Subjects who satisfy the criteria for values of potential clinical concern will be summarised and listed separately. The summary will present the number of subjects with at least one ontreatment visit value (including unscheduled visits) satisfying the criteria. The listing will include all data for the subject and parameter which satisfied the criteria. The record satisfying the criteria will be identified on the listing. The criteria are:

SAP Version v2.0 Page 34 of 43

Date: 16th March 2017

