#### 10.5. VITAL SIGNS

Systolic blood pressure (BP), diastolic BP and pulse will be summarised by visit, time point and treatment group using descriptive statistics for the observed and change from baseline values. Systolic BP, diastolic BP and pulse will be collected in duplicate at each time point. The mean of these 2 measurements will be derived prior to summarizing the data. If a baseline value is missing for a parameter, the screening value will be used as the baseline value. All vital sign data, including the mean values that are summarised, will be listed.

The maximum and minimum values will be derived for each subject over all on-treatment visits (i.e. on or before the date of last study medication plus 1) from all scheduled and unscheduled individual readings and the number (%) of subjects in each of the following categories will be tabulated:

SAP Version v2.0 Page 35 of 43

Date: 16th March 2017

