### 10.6. ECG

The mean of the triplicate measurements will be derived prior to summarizing the data. If a baseline value is missing for a parameter, the screening value will be used as the baseline value.

ECG parameters, and their change from baseline, will be summarised at each time point using descriptive statistics.

For Cohorts 1 and 2, subjects who satisfy the criteria for values of potential clinical concern will be summarised and listed separately. The summary will present the number of subjects with at least one on-treatment (i.e. on or before the date of last study medication plus 1) visit value (including unscheduled visits) satisfying the criteria. The listing will include all data for the subject which satisfies the criteria. The record satisfying the criteria will be identified on the listing. The criteria are:

SAP Version v2.0 Page 36 of 43

Date: 16th March 2017

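### In Cohorts 1 and 2 the laboratory, vital-sign and ECG summaries pool the 10% and 40% BSA groups, although adverse events and PK are split, so an area-dependent effect would be understated in the report.

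*Protocol*

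**What the plan says.** The protocol gives one reporting rule for every cohort. The synopsis states that "within each cohort endpoints will be summarized by treatment group and visit", and Protocol 8.6 repeats it for the three endpoints at issue: "Changes from baseline in laboratory parameters, vital signs and ECG data will be summarized by visit for each treatment group". Neither mentions the area treated.

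The SAP departs from this for some data. For Cohorts 1 and 2, SAP 6.1 says that "adverse events and pharmacokinetic data will be presented by treatment group and BSA treated (10%, 40% and overall) to assess whether BSA impacts this data". SAP 9.1, 9.2 and 10.3 carry the split out (Cohort 1 concentrations are only listed), and SAP 10.2 also splits ointment volume and amount by BSA treated.

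The other safety sections contain no such split:

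- Laboratory tests (SAP 10.4): haematology, chemistry and "continuous urinalysis parameters will be summarised by treatment group using descriptive statistics".
- Vital signs (SAP 10.5): blood pressure and pulse "will be summarised by visit, time point and treatment group using descriptive statistics".
- ECG (SAP 10.6): "ECG parameters, and their change from baseline, will be summarised at each time point using descriptive statistics". Treatment group and cohort follow from the general rule in SAP 6.1.

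The index of tables (SAP 14) agrees. Adverse events have tables dedicated to Cohorts 1 and 2, while the laboratory, vital-sign and main ECG tables are single by-cohort tables covering all three cohorts. SAP 12, which lists changes from the protocol, gives no reason for treating the two kinds of safety data differently.

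Protocol 2.4 names vital signs, ECG and laboratory tests as primary endpoints in both Cohort 1 and Cohort 2.

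**The concern.** Each of these cohorts contains two planned exposure levels of the same ointment. Protocol Table 2 counts the percentage of BSA covered as part of the dosing regimen, and its volume limits differ fourfold between the two areas: 1.25 to 5 mL per application at 10% BSA, 5 to 20 mL at 40%. Treated area is thus the main planned exposure contrast among the active subjects. The SAP states that it wants to know whether area matters, and then arranges to look in only two types of data.

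A quarter of each active column (2 of 8) comes from subjects treated over a quarter of the area. A mean shift that grows with area would look smaller in the table than it was at 40% BSA, and the table could not show the gradient. Cohort 3 may be treated over up to 50% BSA, so the 40% result is the closest in-patient evidence for it. At stake is how clearly the study report describes systemic safety at 40% BSA. No error rate is involved, because no testing is planned in Cohorts 1 and 2 (Protocol 8.2).

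**Working it through.** **Group sizes (Protocol 3.1).** Sentinels: 3 subjects at 2:1, giving 2 active and 1 placebo, at 10% BSA. Remainder: 9 subjects at 2:1, giving 6 active and 3 placebo, at 40% BSA. Total 3 + 9 = 12, which reproduces the planned cohort size. The pooled columns hold 2 + 6 = 8 active and 1 + 3 = 4 placebo.

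**Assumption.** Let r be the effect at 10% BSA divided by the effect at 40% BSA. The documents do not give r, so a range is shown: 0 (effect only at 40%), 0.25 (proportional to area), 0.5, and 1 (no dependence on area).

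**Share of the 40% BSA effect visible in the pooled active mean:** (n40 + r × n10) / (n40 + n10).

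| r | Planned sizes (6 and 2 active) | Minimum 40% set plus sentinels (4 and 2 active) |
|---|---|---|
| 0 | 6/8 = 75% | 4/6 = 67% |
| 0.25 | 6.5/8 = 81% | 4.5/6 = 75% |
| 0.5 | 7/8 = 88% | 5/6 = 83% |
| 1 | 100% | 100% |

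The last column uses the smallest 40% BSA data set that allows progression, 4 active and 2 placebo (Protocol Table 4).

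**Counts.** If values of clinical concern arose in 2 of the 6 active subjects at 40% and in neither sentinel, the pooled table would show 2/8 = 25% instead of 2/6 = 33%.

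**What pooling gains in precision.** Assume a common SD and no effect of area on placebo. In SD units, effect over standard error is 1/√(1/6 + 1/3) = 1.414 for the 40% groups alone. Pooled, it is the visible share divided by √(1/8 + 1/4):

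- r = 0: 1.225, a 13% loss.
- r = 0.25: 1.327, a 6% loss.
- r = 0.5: 1.429, a 1% gain.
- r = 1: 1.633, a 15% gain.

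Pooling therefore costs signal when r is small and helps when r is large. That is a reason to show both the split and the overall column.

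**Which r is plausible.** In Cohort 1 the treated skin is healthy, and the treated-area ratio is 10/40 = 0.25. In Cohort 2 the lesional area may matter more. The example body maps in Protocol Appendices 6 and 7 both show a patient with 20% of BSA affected, one treated over 10% and the other over 40%. If uptake is mainly through lesional skin (an assumption), the contrast is 10% against 20%, so r is about 0.5. Protocol 6.3 also says up to 40% for this group, so even the fourfold area contrast is not fixed.

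**The case against.** The strongest reply is that little of consequence hangs on these tables. Four parts of it deserve an answer.

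**Progression.** A reader might infer that decisions to open the next cohort rest on diluted figures. The documents do not support that. Under Protocol 3.7.1, laboratory, ECG and vital-sign findings count when they occur in an individual actively treated subject. The skin criteria count only subjects dosed over 40% BSA, and complete data at 40% BSA are required. Sentinels are reviewed before dosing at 40% starts (Protocol 3.5). The PK criterion does use a cohort mean, but of AUC, and not from these tables. SAP v2.0 already refers to the outcome of the Cohort 1 and Cohort 2 safety reviews (SAP 4.5 and 12), so its tables cannot alter those decisions. This part of the objection stands in full.

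**Extent.** A reader might also infer that every exposure-related change is diluted. That is too strong. Dilution needs an effect that is smaller at 10% BSA, and a finding in a sentinel or one unrelated to area is not understated. Nor is the active column meant to describe 40% BSA alone: the primary objective in Protocol 2.1 names no BSA level. This stands too.

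**Recoverability.** All data are listed. Laboratory and ECG values of concern (ECG in Cohorts 1 and 2) are summarised and listed separately, and vital-sign listings flag them. With two active sentinels per cohort, matching a flagged subject to the area treated is easy. This stands for individual extremes. It does not replace a summary for modest mean shifts below the flagging limits, and only the plasma concentration listing is expressly said to carry BSA treated (SAP 9.1).

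**Information gained.** The 10% columns would hold 2 active subjects and 1 placebo subject, and 2/6 against 2/8 is far too imprecise to separate. Exposure was reported as low and intermittent in both cohorts (SAP 12), which lowers the chance of seeing a gradient. That is true, but the SAP accepts columns of the same size for adverse events, and the main gain is an unmixed 40% column.

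**Conclusion.** The inconsistency is real and the SAP does not resolve it. It splits adverse events and PK by area treated so as to judge whether area matters, and leaves three other primary safety endpoints of the same cohorts pooled.

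At the planned sizes, the pooled active mean understates the 40% BSA effect by 25% (r = 0), 19% (r = 0.25) or 12.5% (r = 0.5), and not at all if area has no influence. With only the minimum 40% data set, the largest understatement is 33%. These figures rest on the assumed r; in Cohort 2 a value near 0.5 is as defensible as 0.25.

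The effect is on the descriptive safety results in the study report. The progression decisions are untouched, and individual values remain listed. This is a worthwhile and cheap improvement in reporting, not a defect in subject protection or in inference.

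**What to change.** Amend the sentence in SAP 6.1 so that, for Cohorts 1 and 2, the 10%, 40% and overall presentation also covers the laboratory, vital-sign and ECG summaries (tables 14.3.4.x and 14.3.5.x). Keep the overall column, add BSA treated to the corresponding listings, and use the 40% column for statements about safety at 40% BSA. Cohort 3 output is unchanged.

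SAP 2 permits amendments before database lock. After lock, the same tables can be added and documented in the study report as additional analyses.

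The cost is one sentence and extra columns, in a layout already specified for the adverse event tables. The tables become wider, and the 10% columns, with 2 active subjects and 1 placebo subject, should be labelled as descriptive only.
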